17.5.10. Chronic lung disease 36 weeks postmenstrual age

17.5.10.1. Derivation

This is a binary outcome with a "Yes/No" response and can be found on CRF "Form 7a: Clinical

Outcomes" under section 6 for the question "Bronchopulmonary dysplasia". It should be noted

that Form 7a is completed each time a baby is transferred and so there may be more than one

"Form 7a" for each baby. If "Yes" is selected on any completed 'Form 7a' then the outcome is

"Yes" for that baby, if "No" is selected on all forms then the outcome is "No".

17.5.10.2. Analysis

The analysis will use the method of Fisher's exact test to compare proportions in the standard

group compared to the impregnated group and relative risks will be presented with 95%

confidence intervals.

17.5.11. Necrotizing enterocolitis (NEC): Bell's stage II or III

17.5.11.1. Derivation

This is a binary outcome with a "Yes/No" response and can be found on CRF "Form 7a: Clinical

Outcomes" under Section 5. It should be noted that Form 7a is completed each time a baby

is transferred and so there may be more than one "Form 7a" for each baby. If "Yes" is selected

on any completed 'Form 7a' then the outcome is "Yes" for that baby, if "No" is selected on all

forms then the outcome is "No".

17.5.11.2. Analysis

The analysis will use the method of Fisher's exact test to compare proportions in the standard

group compared to the impregnated group and relative risks will be presented with 95%

confidence intervals.

17.5.12. Treatment for retinopathy of prematurity

17.5.12.1. Any treatment given

17.5.12.1.1 Derivation

This is a binary outcome with a "Yes/No" response and can be found on CRF "Form 7a: Clinical

Outcomes" under section 6. It should be noted that Form 7a is completed each time a baby is

transferred and so there may be more than one "Form 7a" for each baby. If "Yes" is selected

on any completed 'Form 7a' then the outcome is "Yes" for that baby, if "No" is selected on all

forms then the outcome is "No".

17.5.12.1.2 Analysis

The analysis will use the method of Fisher's exact test to compare proportions in the standard

group compared to the impregnated group and relative risks will be presented with 95%

confidence intervals.

17.5.12.2. Type of treatment given

17.5.12.2.1 **Derivation**

If "Yes" is selected for the question "Retinopathy of prematurity treatment medically or

surgically" then the type of treatment is given as either "Laser", "Cryotherapy" or "Injection".

17.5.12.2.2 Analysis

This data will be presented descriptively with frequency tables split by treatment arm. No

formal statistical analysis will be undertaken.

17.5.13. Abnormalities on cranial ultrasound

17.5.13.1. Derivation

This is a binary outcome with a "Yes/No" response based on the following two clinical

outcomes:

Periventricular leukomalacia

• Intracranial haemorrhage detected on head ultrasound

Each of these can be answered with a "Yes/No" response and can be found on CRF "Form

7a: Clinical Outcomes" under section 6 for the questions 3/4/4a. It should be noted that Form

7a is completed each time a baby is transferred and so there may be more than one "Form

7a" for each baby. If "Yes" is selected on any completed 'Form 7a' then the outcome is "Yes"

for that baby, if "No" is selected on all forms then the outcome is "No". Where babies

experience intracranial haemorrhage, the worst grade that is observed will also be reported.

17.5.13.2. Analysis

The analysis will use the method of Fisher's exact test to compare proportions in the standard

group compared to the impregnated group and relative risks will be presented with 95%

confidence intervals. No testing will be conducted in relation to the grade of IVH that was

experienced.

17.5.14. Time to full milk feeds after randomisation

17.5.14.1. Derivation

Whether a baby reached full milk feeds is captured on CRF "Form 7a: Clinical Outcomes".

The date that the baby first reached full milk feed is recorded alongside this. The date of

randomisation is recorded on CRF "Form 2: Randomisation". The amount of days between

randomisation and full milk feeds can be calculated from this. It should be noted that Form 7a

is completed each time a baby is transferred and so there may be more than one "Form 7a"

for each baby. If there are multiple dates for the baby reaching full milk feeds on the different

forms, the first date will be used.

17.5.14.2. Analysis

The survival analysis will use the method of the Log rank test and Cox proportional hazard

regression models if appropriate. Results will be presented using Hazard Ratios and 95%

confidence intervals. Kaplan-Meier curves stratified by treatment will be presented. Survival

times will be measured from the date of randomisation to the date of full milk feeds.

If a baby has already reached full milk feeds at randomisation then they will be excluded from

this outcome. If a baby does not reach full milk feeds then they will be censored at the last

observation recorded.

17.5.15. Total duration of parenteral nutrition from randomisation until discharge

from NNU

17.5.15.1. Derivation

The total number of calendar days of parenteral nutrition can be found on CRF "Form 7a:

Clinical Outcomes" under section 7. As each baby may have more than one 'Form 7a'

completed, the overall total number of days should be summed across all 'Form 7a's returned.

Sites should only be recording the amount of days on full milk feeds at that hospital. A check

will be performed to ensure that the number of days on full milk feeds does not exceed the

number of days spent at that hospital.

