9.2. Secondary outcomes

Outcomes captured up until 48 hours after PICC removal:

1. Rifampicin resistance in any isolate from blood/CSF culture.

2. Rifampicin resistance in any isolate from PICC tips.

3. Type of organism isolated from BSI.

4. Rate of BSI per 1000 PICC-days (including recurrent BSI).

5. Occurrence of 1 or more BSI.

6. Rate of catheter-related BSI per 1000 PICC days.

7. Rate of blood/CSF culture sampling per 1000 PICC days.

8. Duration of antimicrobial exposure from randomisation up to 48 hours after PICC

removal.

9. Time to PICC removal.

Outcomes captured up until discharge home from neonatal care/death/6 months post

randomisation:

10. Chronic lung disease 36 weeks postmenstrual age.

11. Necrotizing enterocolitis (NEC): Bell's stage II or III.

12. Treatment for retinopathy of prematurity.

13. Abnormalities on cranial ultrasound.

14. Time to full milk feeds after randomisation.

15. Total duration of parenteral nutrition from randomisation until discharge from NNU.

16. Death:

a) within 6 months (26 weeks) of randomisation

b) before discharge home from neonatal care

c) time to death

10. Determination of Sample Size

The sample size calculation can be found in section 9.4 of the protocol.

11. Study Framework

The overall objective for each of the study outcomes (primary and secondary) is to test the

superiority of AM-PICCs compared with S-PICCs.

12. Confidence Intervals, p-values and Multiplicity

All applicable statistical tests will be two-sided and will be performed using a 5% significance

level; confidence intervals presented will be 95%. No adjustment will be made for multiplicity

for the secondary outcomes. Percentages will be presented as 1 decimal place. Test statistics,

p-values, confidence intervals and measures of spread will be presented as 2 decimal places.

13. Timing and Objectives of Interim and Final Analyses

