17.5.15.2. Analysis

The analysis will use the method of the two sample t test or Mann Whitney U test depending

on the distribution of the data. Means will be presented with 95% confidence intervals or

medians and interquartile range as appropriate.

The proportion of days in the primary outcome time window spent on parenteral nutrition will

be reported.

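### The parenteral-nutrition derivation (SAP 17.5.15.1) switches to days on full milk feeds for its per-hospital recording rule and its plausibility check, so the check does not bound the days being summed

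*SAP*

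**What the plan says.** Section 9.2 lists the outcome as "15. Total duration of parenteral nutrition from randomisation until discharge from NNU". Section 17.5.15.1 begins with the matching variable: "The total number of calendar days of parenteral nutrition can be found on CRF" Form 7a, in section 7 of that form. Because a baby may have more than one of these forms "completed, the overall total number of days should be summed across all 'Form 7a's returned".

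Two sentences on data quality follow, and both name something else. The first says what each hospital is expected to enter: "Sites should only be recording the amount of days on full milk feeds at that hospital". The second says that a check "will be performed to ensure that the number of days on full milk feeds does not exceed the" length of stay at that hospital.

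Section 17.5.15.2 then returns to parenteral nutrition: "The proportion of days in the primary outcome time window spent on parenteral nutrition will" be reported, alongside a t test or Mann-Whitney comparison of the totals.

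**The concern.** Form 7a is completed at every transfer and the totals are added up, so the sum is right only if each form covers that hospital's own days. If a receiving hospital enters a cumulative figure, the earlier days are counted twice. The two sentences are evidently there to guard against this, but they apply the safeguard to a quantity that is not being summed. A programmer who follows the text literally would leave the PN entries without any check against length of stay.

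What is at stake is the accuracy of PN duration, a secondary outcome, in babies who moved between hospitals. Section 21 describes independent programming of the primary analysis only, so the SAP provides no second derivation of this outcome that might expose the slip.

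**Working it through.** No figure in the plan needs reproducing. The check is to set the statements side by side.

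| Place in the SAP | Role | Variable named |
|---|---|---|
| 9.2, outcome 15, and heading of 17.5.15 | Outcome | Parenteral nutrition |
| 17.5.15.1, opening sentence | Source field | Parenteral nutrition, calendar days |
| 17.5.15.1, second sentence | Summing over forms | The same total |
| 17.5.15.1, third sentence | What each hospital records | Full milk feeds |
| 17.5.15.1, fourth sentence | Plausibility check | Full milk feeds |
| 17.5.15.2 | Analysis | Parenteral nutrition |

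**Could the milk-feed check be a deliberate extra check?** Three things speak against it.

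- Section 17.5.14.1, which covers full milk feeds, describes whether they were reached and one date: "The date that the baby first reached full milk feed is recorded alongside this". The SAP describes no count of days on full milk feeds, so the check refers to a quantity it defines nowhere else.
- When several Forms 7a give different dates for full feeds, section 17.5.14.1 takes the first. Nothing is summed there, so that outcome needs no limit to each hospital's own days.
- Such a limit does make sense for the quantity that is summed across forms, which is PN days.

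The likeliest explanation is a term carried over from the neighbouring section.

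**What the check does as worded.** For each form, let P be the PN days entered, M the days on full milk feeds, and S the days spent at that hospital.

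- Intended condition: P ≤ S.
- Written condition: M ≤ S.

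The written condition does not contain P, so no value of P can make it fail.

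**Hypothetical example (all three numbers assumed, none from the SAP).** Take S = 30, M = 10, and P = 45 because days at an earlier hospital were included.

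- Written check: 10 ≤ 30, passes.
- Intended check: 45 > 30, fails. At least 45 − 30 = 15 of the days entered cannot belong to that stay.

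The example shows only the logic. It says nothing about how often such entries occur.

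**The case against.** The strongest reply is that this is a self-revealing slip. The source field, the summing rule, the title and the analysis all name PN. The SAP describes no count of milk-feed days on which to run the check. A sensible programmer would therefore read it as PN days against length of stay. That reply stands as far as the definition of the outcome goes. A reader might infer from the two sentences that the outcome is built on the wrong variable; the opening of the same section rules that out.

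A reader might also infer that sites were told to enter the wrong quantity. The SAP does not support this. Section 5 describes analyses performed by the trial statistician, and the sentence tells the analyst what the entries should contain. Sites would have reported milk-feed days only if Form 7a or its completion guidance carried the same slip, and neither is at hand.

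It is also fair to say that data-management checks outside the SAP may already cover PN days, and that nothing in the SAP suggests carry-over errors would differ between arms.

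What the reply does not remove is that the one check the SAP specifies for this outcome names the wrong quantity. A plan should not depend on its reader repairing it.

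**Conclusion.** Section 17.5.15.1 contradicts itself and needs correcting. As written, its plausibility check does not bound the PN days that are summed, so that check would not detect days carried over from an earlier hospital.

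The consequence is limited to one of 16 listed secondary outcomes; the primary outcome is untouched. Its size cannot be judged from the SAP, which gives neither the number of babies with more than one Form 7a nor any rate of entry error. The conclusion rests on the literal wording and on the assumption that the check was meant for the quantity being summed. It does not show that any total is wrong, or that the comparison between arms is biased.

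**What to change.** - In both sentences of 17.5.15.1, replace days on full milk feeds with days of parenteral nutrition.
- Run the check as PN days on each Form 7a against days spent at that hospital, and query failures before the data are frozen.
- Confirm that the Form 7a section 7 field and its completion guidance ask for PN days at that hospital only. This matters because even the corrected check is only an upper bound: carry-over that leaves the entry at or below the length of stay still passes.

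The cost is two wording changes, one programmed check and a look at the form and its guidance. No new data are needed beyond answers to any queries. A rule on counting the day of transfer is not proposed here: the SAP describes a total per form, not dated PN days, so it does not show that such overlap could be identified.

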17.2. Demographic and Other Baseline Characteristics

The comparability of the two randomised groups with respect to the baseline clinical factors

of the following will be presented

Gender

Birth weight in grams (categories of <750, 750 – <1000, 1000 - <1250, 1250 –

<1500, 1500 - <1750, 1750 - < 2000 and ≥2000)

- Gestational age in weeks (categories of <26, 26 <28, 28 <30, 30 <32, 32 <34, 34 <36, 36 <38, ≥38). Note: This will be estimated by calculating the difference in weeks between the baby's date of birth and final estimated date of delivery. It will be assumed that the final estimated date of delivery will be 40 weeks. Weeks are complete weeks, for example "36 weeks" would mean 36 weeks plus anything up to and including 6 days.
- Major congenital anomaly
- Age at randomisation in days (categories of <2, 2 <7, 7 <14,, 14 < 21, 21 < 28 ≥28). Note: "<2 days" = "<48 hours".
- Location of birth (categories of 'inborn' and 'Baby transferred to the study hospital after birth)
- Mode of delivery (categories of 'vaginal' and 'caesarean')
- Membranes ruptured more than 24 hours before delivery (Yes/No)
- Apgar score at 5 minutes (categories of 0 3, 4 7, 8 10)
- Maternal antenatal corticosteroids (Yes/No)
- Maternal antibiotics within 12 hours prior to delivery (Yes/No)
- Surgery before randomisation (categories of 'longer than 6 days ago', 'within the last 6 days' and 'no surgery'
- Positive blood culture within 72 hours prior to randomisation (Yes/No) taken from microbiology form
- Antibiotics or antifungals within 72 hours prior to randomisation excluding Prophylaxis (Yes/No). Note: See table below for details on classifying this from information in section 5 of CRF "Form 3: Baby Characteristics"

Questions on Form 3:	Baby classified as		
1: IV antibiotics	2: IV and/or enteral	2a: If yes, was the	having "Antibiotics
within 72 hours prior	antifungal	antifungal for	or antifungals within
to randomisation?	medication within 72	prophylaxis only?	72 hours prior to
	hours prior to		randomisation"
	randomisation?		
Yes	Yes	No	Yes
Yes	Yes	Yes	Yes
Yes	No	N/A	Yes
No	Yes	No	Yes
No	Yes	Yes	No
No	No	N/A	No

Number of devices in situ at randomisation (<4, ≥4)

Respiratory support (categories of 'None', 'ET Tube', 'Non-invasive ventilation', and

'Oxygen')

PICC insertion site (categories of 'No line inserted', 'Lower limb', 'Upper limb', 'Scalp',

'Other').

All comparisons between the groups will be descriptive in nature and no formal hypothesis

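### Parenteral-nutrition duration is defined from randomisation but derived without that start point, and the accompanying check names the wrong variable and the wrong period

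*SAP*

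**What the plan says.** The outcome list in SAP 9.2 gives "15. Total duration of parenteral nutrition from randomisation until discharge from NNU", and the analysis section repeats this start point in its heading: "17.5.15. Total duration of parenteral nutrition from randomisation until discharge".

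The derivation in 17.5.15.1 then does three things.

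- **Source and sum.** It says "The total number of calendar days of parenteral nutrition can be found on CRF" Form 7a, section 7. Because a baby may have several such forms, it adds that "completed, the overall total number of days should be summed across all 'Form 7a's returned". Neither sentence mentions randomisation.
- **Recording rule.** "Sites should only be recording the amount of days on full milk feeds at that hospital".
- **Check.** The upper limit is the "number of days spent at that hospital". The quantity compared with it is not PN: the check "will be performed to ensure that the number of days on full milk feeds does not exceed the" limit.

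The analysis (17.5.15.2) is a two-sample t test or a Mann-Whitney U test, so the outcome is formally compared between arms.

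**The concern.** The definition fixes the start of the count at randomisation, and the derivation does not carry that start point through. The two sentences that should protect the count refer to another variable, and they use the whole hospital stay as the period. A programmer following 17.5.15.1 literally would sum whatever is on the forms and test milk-feed days against length of stay. Nothing would be done to test PN days.

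For the hospital where the baby was randomised, the stay begins at birth or admission. Section 17.2 tabulates age at randomisation in bands from under 2 days to 28 days or more, so the SAP foresees time in hospital before entry. PN given in that time cannot have been affected by the trial line. If it is counted, the reported quantity is not the outcome named in 9.2.

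**Working it through.** The SAP states no figure for this outcome, so there is nothing to reproduce. The check is a comparison of the text, followed by illustrations on assumed values.

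**1. Definition against derivation**

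| Element | 9.2 and 17.5.15 heading | 17.5.15.1 |
|---|---|---|
| Quantity | PN days | PN days in the source sentence; days on full milk feeds in the recording rule and the check |
| Start | Randomisation | Not stated |
| Upper limit in the check | Implied: stay since randomisation | Whole stay at that hospital |

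Neighbouring derivations do state the start. Time to PICC removal (17.5.9.1) and time to full milk feeds (17.5.14.1) both take the randomisation date from Form 2 and count from it.

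**2. Would earlier PN days be detected?** Read literally, no, because PN days are not checked. Suppose the check is read as meant for PN. Assume 10 PN days and a 50-day stay after randomisation, so the intended count is 10.

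| Stay before randomisation | PN days before | Recorded total | Whole-stay limit | Limit since randomisation |
|---|---|---|---|---|
| 1 | 1 | 11 | 51, passes | 50, passes |
| 5 | 4 | 14 | 55, passes | 50, passes |
| 14 | 12 | 22 | 64, passes | 50, passes |
| 28 | 24 | 34 | 78, passes | 50, passes |

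The whole-stay limit misses all four. The tighter limit also misses them, because it responds only when the recorded total exceeds the stay after randomisation. It does add something when that stay is short. With 12 PN days in a 14-day stay before randomisation, and 10 PN days in a 12-day stay after it, the total of 22 passes the whole-stay limit of 26 but fails the limit of 12.

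**3. Effect on the comparison, if earlier days enter.** Let r be the SD of PN days before randomisation divided by the SD of PN days after it, and take the two as independent. For a difference in means:

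- SE ratio = √(1 + r²)
- relative efficiency = 1/(1 + r²)
- power, for a comparison that would have 80%, ≈ Φ(2.802/√(1 + r²) − 1.960), where 2.802 = 1.960 + 0.842

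| Assumed r | Relative efficiency | Power |
|---|---|---|
| 0.1 | 0.99 | 79.6% |
| 0.25 | 0.94 | 77.6% |
| 0.5 | 0.80 | 70.7% |
| 1.0 | 0.50 | 50.8% |

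In days, assumed SDs after and before randomisation of (10, 3), (15, 5) and (12, 8) give SE ratios of √109/10 = 1.044, √250/15 = 1.054 and √208/12 = 1.202. The corresponding losses of effective sample (1 − 1/ratio²) are 8%, 10% and 31%.

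These values show how the result depends on r; they are not estimates for this trial. With correlation ρ between earlier and later days, the variance factor is 1 + r² + 2ρr, which falls below 1 when ρ < −r/2. Under independence precision falls; without that assumption even the direction is open.

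**The case against.** The strongest reply is that the SAP states the start point twice, once in the heading directly above the derivation. On that view 17.5.15.1 only says where the number is found. The number is a field on Form 7a, which is not shown and may itself ask for days since randomisation. If it does, no earlier day enters and the gap is one of wording. This part stands: the text leaves the error possible and does not show that it occurs.

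A reader might infer more than the text supports in four ways.

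- **That PN days are checked against length of stay.** They are not. The sentence names days on full milk feeds, so as written PN has no check.
- **That PN before randomisation is certainly counted.** This depends on the form. The age bands in 17.2 show that late randomisation is possible, not how common it is or how much PN came first.
- **That the comparison is biased.** Days before allocation are balanced between arms in expectation.
- **That a definite share of the sample is lost.** The SDs and the independence are assumed, and the formula is for a difference in means, whereas 17.5.15.2 may use Mann-Whitney.

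The reply does not remove the error in the check. Even if the form is correctly anchored, the recording rule and the check name the wrong variable, and the limit would accept totals that are impossible under the definition in 9.2.

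**Conclusion.** The point holds as a minor correction to one secondary outcome, number 15 of 16. Two faults are visible in the SAP alone: the derivation has no randomisation start, and the recording rule and check refer to milk feeds over the whole stay, leaving PN days without a valid check.

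The consequence is conditional. Unless section 7 of Form 7a already asks for days since randomisation, PN given earlier at the randomising hospital can be counted. Mean duration in each arm would then be overstated by that arm's mean number of PN days before randomisation, and precision may fall by an amount that the SAP does not allow to be computed. No bias between arms is expected, and the primary outcome is unaffected.

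**What to change.** In 17.5.15.1:

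1. Replace full milk feeds with parenteral nutrition in both the recording rule and the check.
2. State that only calendar days of PN on or after the date of randomisation count, and confirm that section 7 of Form 7a asks for this.
3. Check that PN days on each form do not exceed the days at that hospital from the later of randomisation and admission until the baby leaves. Query forms that fail.

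The cost is a few sentences, one programmed check using dates already collected, and a small number of data queries. The check is a supplement, since it finds only totals larger than the stay after randomisation. If the form turns out to be unanchored, SAP wording cannot separate the days, and sites must be asked for the count since randomisation. That would be the larger cost.
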